## 7.7 Premature Discontinuation Visit (if applicable)

The following activities will be performed (if the LAR agrees) should a premature discontinuation occur:

- Obtain interim medical history and note any changes since the last visit.
- Record concomitant medications.
- Symptom-directed physical examination, if needed.
- Vital signs: temperature and pulse.
- Examine placebo microneedle patch application site. Subjects with localized rash, scarring or evidence of secondary infection at placebo microneedle patch application site are to be evaluated by a study investigator. Per investigator discretion, photographic documentation (refer to MOP) and dermatologic referrals may be obtained.
- Study personnel will review the memory aid information with the LAR and record all AE/SAEs.
- The follow-up acceptability questionnaire will be completed by the LAR.

## 7.8 Unscheduled Visit (if needed)

The following activities will be performed should an unscheduled visit occur:

- Obtain interim medical history and note any changes since the last visit.
- Record concomitant medications.
- Symptom-directed physical examination, if needed.
- Vital signs: temperature and pulse.

- Examine placebo microneedle patch application site. Subjects with localized rash, scarring or evidence of secondary infection at placebo microneedle patch application site are to be evaluated by a study investigator. Per investigator discretion, photographic documentation (refer to MOP) and dermatologic referrals may be obtained.
- Study personnel will review the memory aid information with the LAR and record all AE/SAEs.
- The follow-up acceptability questionnaire will be completed by the LAR.

## **8 STUDY PROCEDURES/EVALUATIONS**

### **8.1 Clinical Evaluations**

#### **8.1.1 Medical History**

A complete medical history will be obtained by direct interview with the LAR. LAR(s) will be asked about any history in their infant or young child of significant medical disorders of the head, eyes, ears, nose, throat, mouth, cardiovascular system, respiratory system, gastrointestinal tract, liver, pancreas, kidney, urologic system, nervous system, blood and lymphatics, endocrine system, musculoskeletal system, skin and genit/ reproductive tract. A history of any allergies or hypersensitivities, cancer, immunodeficiency, and autoimmune diseases will be solicited. Interim medical history is also obtained at each clinic visit.

#### **8.1.2 Concomitant Medications**

All medications including prescriptions, over-the-counter medications, vitamins and supplements taken by the subject in the 30 days prior to enrollment should be recorded at the screening visit. Assessment of eligibility will also include a review of permitted and prohibited medications per the exclusion criteria. At subsequent visits, LAR(s) will be queried about changes in their infant or young child's medications. Each new concomitant medication or change to existing medication will be recorded through the Final Study Visit (Day 27 – 38).

Medications which may interfere with the evaluation of the investigational product should not be used during the study unless absolutely necessary. Medications or treatments which are prohibited include:

- Vaccines (unless clinically necessary, vaccines should be avoided within 7 days of enrollment. Live vaccines should not be administered during the study).
- Oral, parenteral or high-dose inhaled steroids.
- Immunosuppressive or cytotoxic therapy.
- Blood products or immunoglobulins.
- Experimental products.

### **8.1.3 Vital Signs**

Vital sign assessments including pulse and temperature will be taken at each in-clinic visit through Day 8 (+2 days) (Day 15 +3 days in those having placebo microneedle patches 2/3 placed).

### **8.1.4 Physical Examination**

A complete physical examination (PE) will be performed at the Day 1 visit. A symptom-directed PE will be performed at all other in-clinic study visits. All PEs will be performed by a clinician licensed to make medical diagnoses and listed on the Form 1572 as the site principal investigator or sub-investigator.

### **8.1.5 Reactogenicity**

The LAR will be provided with a memory aid, thermometer and ruler and will be instructed to record the presence of solicited symptoms and oral temperature through the Day 8 (+2 days) (Day 15 +3 days in those having microneedle patches 2/3 placed).. If a symptom is still present at that time, the LAR will continue to follow that symptom until two days symptom-free. Memory aids will be reviewed and collected by study staff at follow-up visits.

Solicited local microneedle patch application site symptoms include:

- Pain
- Erythema
- Ecchymosis (bruising)
- Induration/swelling
- Pruritus (itching)
- Tenderness

Solicited systemic reactions include:

- Fever
- Irritability (fussiness) above baseline
- Lethargy (drowsiness)
- Decreased appetite
- Vomiting

The LAR will use the following grading scale for describing symptoms:

- Grade 0: Not present
- Grade 1: Mild (present but easily tolerated)
- Grade 2: Moderate (able to tolerate routine activity with effort)
- Grade 3: Severe (unable to continue routine activity)

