### 3.2 Study Endpoints

#### 3.2.1 Primary Endpoints

##### Safety:

- Occurrence of placebo microneedle patch-related serious adverse events from Day 1 through the Final Study Visit (Day 27 – 38).
- Occurrence of Grade 3 placebo microneedle patch-related solicited adverse events for the 8 days following application of the patch.

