##### Reactogenicity:

- Occurrence of solicited application site reactogenicity (e.g., erythema, induration, bruising, itching) for the 8 days following application of the patch.

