Infants and children will be enrolled by sequential age groups using an age de-escalation approach (Table 1). At least 4 infants or children from each Group must complete Day 8 without halting criteria having been met (as detailed in Section 9.5) before subjects will be enrolled into the next younger age group within a Cohort. For Cohort 1, at least the first 2 children in each Group will have the microneedle patch applied to the skin overlying the shoulder blade. If this site is well tolerated without halting criteria having been met (as detailed in Section 9.5), additional microneedle patches may be applied at a different location on the same participant and in subsequent participants to the upper arm, forearm, wrist, thigh, shin, and/or foot. For Cohort 2, microneedle patches may be applied to the

shoulder blade, upper arm, forearm, wrist, thigh, shin, and/or foot. If the first site is well tolerated in the first two children without halting criteria having been met (as detailed in Section 9.5), additional microneedle patches may be applied to the same participants and in subsequent participants.

Table 1: Cohorts and Groups of Enrolled Infants and Young Children			
Cohort	Group Age Range*	Number **	Study Product (administered Day 1 and possibly Day 8)
1	12 – 24 months	Up to 7	Microneedle formulation 1
1	5 – 11 months	Up to 6	Microneedle formulation 1
1	6 weeks – 4 months	Up to 12	Microneedle formulation 1
2	12 – 24 months	Up to 12	Microneedle formulation 2
2	5 – 11 months	Up to 12	Microneedle formulation 2
2	6 weeks – 4 months	Up to 12	Microneedle formulation 2

*\*All age ranges are inclusive. 4 children from each age group must complete Day 8 without halting criteria having been met (as detailed in Section 9.5) before subjects will be enrolled into the next younger age group.*

*\*\* Total number enrolled into each Cohort will be ≤25.*

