### 5.2 Subject Inclusion Criteria

A subject must meet all the following criteria to be eligible to participate in this study:

1. LAR provides written informed consent prior to any study procedures being performed.
2. Subject is between the ages of 6 weeks and 24 months, inclusive, on the day of signing informed consent.
3. Subject is in good health as determined by vital signs, medical history, and a targeted physical examination.
4. LAR is able to understand and comply with required study procedures.

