### **9.2.2 Reactogenicity**

Reactogenicity events are reactions that are common and known to or expected to occur following the administration of the study product. Subjects LAR will be provided with a memory aid, thermometer and ruler and will be instructed to record the presence of solicited symptoms and oral temperature through Day 8 after placebo microneedle

placement (Day 15 in those receiving placebo microneedle patches 2/3). If a symptom is still present at Day 8 (Day 15 in those receiving placebo microneedle patches 2/3), the subject LAR will continue to follow that symptom until two days symptom-free. Memory aids will be reviewed and collected by study staff at follow up visits. Reactogenicity event details will be collected via review of the subject's memory aid and by interview with the subject LAR. Memory aid will not be considered source. The subject memory aid will be reviewed with the subject LAR at subsequent visits. Reactogenicity will be analyzed using Appendices B + C.

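### The home fever instruction specifies oral temperature for children aged 6 weeks to 24 months, and no route is named for clinic readings, the fever exclusion or the fever grades

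*Combined protocol and SAP*

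**What the plan says.** Section 8.1.5 gives the LAR a memory aid, thermometer and ruler, with the instruction to "record the presence of solicited symptoms and oral temperature through the Day 8" (+2 days), extended to Day 15 (+3 days) after patches 2/3. Section 9.2.2 says the same: LARs are "instructed to record the presence of solicited symptoms and oral temperature through Day 8 after placebo microneedle" placement. Neither section has an age exception.

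Inclusion criterion 2 (Section 5.2) sets the population: "Subject is between the ages of 6 weeks and 24 months, inclusive, on the day of signing informed consent". The youngest group in Table 1 (Section 4) is "6 weeks – 4 months", with up to 12 children in each cohort.

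Fever heads the list that Section 8.1.5 introduces with "Solicited systemic reactions include". Appendix C grades it as 100.4 to 101.1 F (Grade 1), 101.2 to 102.1 F (Grade 2) and above 102.1 F (Grade 3). The primary endpoints in Section 3.2.1 include "Occurrence of Grade 3 placebo microneedle patch-related solicited adverse events for the 8 days following application of the patch" and, separately, "Occurrence of solicited application site reactogenicity".

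**The concern.** The only temperature route that the protocol names does not fit the children it enrols. That infants and toddlers cannot reliably give an oral reading is general clinical knowledge and is not stated in the documents. The mismatch between instruction and population is visible in the protocol itself.

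A family that cannot follow the instruction will probably either leave the reading out or use whatever method works. The documents provide no place to record which method was used, and every reading is then graded on one scale that names no route. A fever grade then depends partly on how the temperature was taken.

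At stake are the fever component of the Grade 3 solicited-event endpoint, the bar on patches 2/3 for an ongoing Grade 1 or higher reaction (Section 9.4), and the study halt for a Grade 3 event not clearly due to another cause (Section 9.5). Opening the next younger age group also depends on Section 9.5. If the route is not recorded when the reading is taken, it is unlikely to be recoverable later.

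**Working it through.** **The plan's own figures.** The plan has no calculation on temperature. Its only computed figures are in Section 11.2: with 25 subjects, 34% for one event and 12% for more at a 5% rate, and 38% and 34% at 10%. Exact binomial values for n = 25 are 36.5% and 35.8%, then 19.9% and 72.9%. The printed figures match n = 12 instead (34.1%, 11.8%, 37.7%, 34.1%). That is a separate matter, and the present point does not rest on it.

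**Step 1: route by location.**

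| Place | Use | Route named |
|---|---|---|
| 8.1.5 | Home reading | Oral |
| 9.2.2 | Home reading | Oral |
| 7.1, Appendix A | Thermometer supplied | None, no device type |
| 8.1.3 | Clinic vital signs | None |
| 5.3, criterion 1 | Fever exclusion, >100.4 °F | None |
| Appendix C | Fever grades | None |

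No conversion between routes is given anywhere.

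**Step 2: who is affected.** Cohort 1 maxima in Table 1 are 7 + 6 + 12 = 25. Those under 12 months number 6 + 12 = 18, and 18/25 = 72%. In Cohort 2 each group is capped at 12 and the cohort at 25, so a full cohort has at least 25 − 12 = 13 under 12 months. The remaining children are at most 24 months old at consent.

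**Step 3: which days rest on home readings.** Clinic temperatures fall on Days 1, 2 and 8. On nominal visit days, Days 3 to 7 (five days) have only home readings. After patches 2/3 the clinic days are 9 and 15, leaving Days 10 to 14 (five days).

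**Step 4: spacing of the grades.** Grade 1 to Grade 2: 101.2 − 100.4 = 0.8 F. Grade 2 to the Grade 3 cut-off: 102.1 − 101.2 = 0.9 F, or 1.0 F to the first Grade 3 value (102.2) if readings are in 0.1 F steps. For illustration, assume one route reads 0.3 to 1.0 F below another (not in the documents). A value of 102.2 F (Grade 3) would then read 101.9 to 101.2 F (Grade 2), and 100.4 F (Grade 1) would read 100.1 to 99.4 F (Grade 0).

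**Step 5: path to the endpoints.** There are 6 local and 5 systemic solicited items, 11 in all, and fever is one. It counts toward the primary safety endpoint only at Grade 3 and if judged patch-related. The primary reactogenicity endpoint covers application-site reactions only, so fever does not enter it.

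**Step 6: cost of missing readings, as a range.** Let m be the assumed share of subjects with no usable temperature and p the true rate of a fever event. The chance of seeing at least one in 25 is 1 − [1 − p(1 − m)]^25.

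| m (assumed) | p = 5% | p = 10% |
|---|---|---|
| 0% | 72% | 93% |
| 25% | 62% | 86% |
| 50% | 47% | 72% |
| 72% | 30% | 51% |

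This treats an affected child as contributing nothing. Clinic readings would still catch some fevers, so for a given m the table overstates the loss.

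**The case against.** The best defence is that the protocol is not the only operating document. Section 7.1 says LARs receive instructions with the thermometer, Section 12.2 treats the memory aid as a separate document for the IRB, and Section 10.2 sends form completion to the Manual of Procedures. A workable route may be set there. This does not cure the problem: a different route in those documents would contradict two sections of the protocol, and the same route would repeat the difficulty.

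Second, home readings are not the only fever data. Clinic temperatures are scheduled, LARs are interviewed, and Section 9.2.2 says the memory aid is not source. This stands in part. The Section 9.4 decision concerns an ongoing reaction at the Day 8 visit, when temperature is also taken in clinic, so that rule is partly protected. The days between visits are not, and an interview cannot supply a temperature that was never validly taken.

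Third, the link to a primary endpoint is narrow, Section 9.5 excludes Grade 3 events clearly due to another cause, and the analysis is descriptive. All of that stands and limits the weight of the point.

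A reader might go further and infer that home fever data will be missing or invalid. The documents give no rate of missing readings and nothing on feasibility by age, so likely is as far as one can go. A reader might also divide an assumed route offset by a band width to get a share of misgraded readings. That is not supported either. The offset is not in the documents, mixed routes would shift only some readings, and Grade 3 has no upper limit, so the ratio cannot measure losses across the cut-off that matters for the primary endpoint.

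**Conclusion.** The point holds as a mismatch between a stated instruction and the trial's own population. It is more than missing detail, because the protocol does name a route and that route does not suit children of this age. The likely result is missing, unreliable or mixed-route home fever readings on the days between clinic visits, graded on thresholds 0.8 to 1.0 F apart.

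The consequence is moderate. It reaches one of 11 solicited items, the primary safety endpoint only through Grade 3 patch-related fever, Section 9.5 directly, and Section 9.4 in part. It does not call the primary reactogenicity endpoint into question. The conclusion rests on one premise from outside the documents, that oral readings are generally not workable from 6 weeks to 24 months. The missing-data shares and route offsets above are assumptions that show a range and are not estimates for this trial.

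**What to change.** Before enrolment, reconcile the oral instruction in Sections 8.1.5 and 9.2.2 with the enrolled ages:

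- Name a route, or a route for each age group, that can be taken throughout 6 weeks to 24 months. The choice is for the sponsor and the investigator.
- Apply the same rule to clinic readings in Section 8.1.3.
- Record the route with every reading on the memory aid and CRF.
- State in Appendix C which route the fever bands refer to.

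The cost is wording in four sections, one CRF and memory-aid field, and possibly a different supplied thermometer. No subjects or visits are added.

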#### **8.1.6 Acceptability Assessments:**

To gauge LAR acceptability of vaccination using a microneedle patch, the LAR will complete a survey at Days 1, 2 (+1 day), 8 (+2 days), and Day 27 - 38 (Day 9 (+2 days) and Day 15 (+3 days) in those having placebo microneedle patches 2/3) including items that assess vaccination acceptability items (outcomes) via continuous scales (0-10 likelihood) and vaccination knowledge, attitudes, perceptions, and beliefs using Likert-type measurement (1-5 agreement levels) for multiple time point ANOVA and correlational analyses. The LAR will report on absolute and relative scores of ease of use, pain, product apprehension, comparative product utility, and overall preference comparing placebo microneedle patch application to previous experience with needle and syringe injection (Day 1); preference comparing the post-patch period to prior experience with vaccination (Day 8 (+2 days), and 27 – 38; also Day 9 (+2 days) and Day 15 (+3 days) in those having placebo microneedle patches 2/3); and perception of ease with which they might administer a microneedle patch in the future. The same LAR will complete the survey at all follow-up time points whenever possible. Basic sociodemographic characteristics will also be included, such as race/ethnicity, healthcare utilization/access, parental educational attainment, healthcare experience including previous immunization history, and socioeconomic indicators (household income, education).

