### 7.3 Visit 3: Day 8 (+2), Clinic Visit

The following assessments will be performed.

- Obtain interim medical history and note any changes since the last visit.
- Record concomitant medications.
- Symptom-directed physical examination, if needed.
- Vital signs: temperature and pulse.
- Examine placebo microneedle patch application site. Subjects with localized rash, scarring or evidence of secondary infection at microneedle patch application site are to be evaluated by a study investigator. Per investigator discretion, photographic documentation (refer to MOP) and dermatologic referrals may be initiated for subjects with localized reactions.
- Study personnel will review the memory aid information with the LAR and record all AE/SAEs. If symptoms persist, clinic staff will attempt to follow up with the subject daily until two days symptom-free. Maximum severity post Day 8 and stop date of the symptoms will be recorded by clinic staff on the Solicited Events eCRF.
- The follow-up acceptability questionnaire will be completed by the LAR. The LARs of subjects who have no ongoing solicited or unsolicited general AE or local AEs will have the opportunity to decide to have second and third placebo microneedle patches placed at different body sites from the initial location.
- Subjects with solicited or unsolicited general AE or local AEs or declining the optional microneedle patch 2/3 will then proceed to the Final Study Visit (Days 27 – 38).

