## **9.4 Individual Halting Rules**

Enrolled subjects will not be eligible to receive placebo microneedle patches 2/3 placement at Day 8 (+2 days) if any of the following occur:

- An ongoing  $\geq$ Grade 1 local site reaction (see Appendix B).
- An ongoing  $\geq$ Grade 1 solicited general AE (see Appendix C) or unsolicited AE.

Subjects unable to receive placebo microneedle patches 2/3 due to meeting an individual halting rule will continue to follow up according to the protocol through Day 27 – 38.

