## 14 SUPPLEMENTS/APPENDICES

### 14.1 Appendix A: Study Schedule

Visit #	1	2	3	4 &	5 &	Final*		
Procedures	D1	D2 +1	D8 +2	D9 +2	D15 +3	D27 - D38	Unscheduled Visit (If needed)	Premature Discontinuation
Signed Consent Form	X							
Inclusion/Exclusion Review	X							
Complete Medical History	X							
Concomitant Medications	X	X	X	X &	X &	X	X	X
Interim Medical History		X	X	X &	X &	X	X	X
Sign Optional Consent For Microneedle Patch 2/3	(X )		(X)					
Application of microneedle patch	X		X &					
Distribute memory aid, ruler & thermometer	X		X &					
Review memory aid		X	X	X &	X &	(X)	(X)	(X)
Physical Exam	Complete Physical Exam	X						
	Assessment of microneedle patch application site	X* *	X	X* *&	X &	X &	X	X
	Symptom-Directed Physical Exam		(X)	(X)	(X) &	(X) &	(X)	(X)
	Height and weight	X						
	Vital Signs ^	X	X	X	(X) &	(X) &	X	X
Photograph site of placebo microneedle patch	(X )	(X)	(X)	(X)	(X)	(X)	(X)	(X)
Assessment of Adverse Events and SAEs	X* *	X	X	(X) &	(X) &	X	X	X
Acceptability Questionnaire	X	X	X	(X) &	(X) &	X	X	X

\* The final study visit will be a telephone call at D27 – D38

\*\* Occurring 15 minutes and 30 minutes after microneedle patch removal.

& At Day 8 the LARs of subjects who no ongoing solicited or unsolicited general AE or local AEs will have the opportunity to decide to have second and third placebo microneedle patches placed at different body sites from the initial location. In those that elect to have a second/third placebo microneedle patch placed, they will return for clinic visits on Day 9 and Day 15.

^ Vital signs will include temperature and pulse.

(X) – As indicated/appropriate.

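### Does the change of preference question after Day 1 in Section 8.1.6 undermine the planned multiple time point ANOVA of the acceptability survey?

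*Combined protocol and SAP*

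**What the plan says.** Section 8.1.6 schedules the survey for all LARs on Days 1, 2, 8 and 27–38, and also on Days 9 and 15 for those whose child has patches 2/3. Its first sentence names two kinds of item: acceptability outcomes on 0–10 likelihood scales, and knowledge, attitude and belief items on 1–5 agreement scales. It closes by saying these are "for multiple time point ANOVA and correlational analyses".

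The second sentence lists further scores the LAR will report. For Day 1 the list ends with "overall preference comparing placebo microneedle patch application to previous experience with needle and syringe injection (Day 1". It then moves to "preference comparing the post-patch period to prior experience with vaccination (Day 8 (+2 days", names the final contact as well, and adds "also Day 9 (+2 days) and Day 15 (+3 days) in those having placebo microneedle patches 2/3". Day 2 is not named for either comparison. The section also says: "The same LAR will complete the survey at all follow-up time points whenever possible".

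Entry to the patch 2/3 subset is restricted. Section 7.3 says "The LARs of subjects who have no ongoing solicited or unsolicited general AE or local AEs will have the opportunity to decide" on further patches. Section 9.4 bars children with an ongoing reaction or AE of Grade 1 or higher: "Enrolled subjects will not be eligible to receive placebo microneedle patches 2/3 placement at Day 8 (+2 days) if any of the following occur". Under Appendix A, those who opt in are the ones for whom "they will return for clinic visits on Day 9 and Day 15".

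Sections 3.2.2 and 11.1 make the survey endpoint a secondary quantitative and qualitative description. The secondary-endpoint text in Section 11.3 covers unsolicited AEs and new-onset conditions only.

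**The concern.** Read together, the two sentences of Section 8.1.6 can suggest that preference is one of the scores to be followed by ANOVA. On that reading there is a real difficulty. Day 1 rates the application of the patch against needle and syringe. Later days rate the period after the patch against prior vaccination. Only Day 8 and the final call put the same preference question to every LAR. A third day could come only from Day 1, which asks something else, or from Days 9 and 15, which exist only for LARs who chose more patches and whose child had no ongoing AE. That subset is selected on tolerability as well as willingness, and both plausibly relate to acceptability.

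At stake would be a reported change in preference over time that is only a change of question or of respondents. Acceptability is in the study title, and Section 2.3.2 says the results will inform a later infant vaccine trial. Section 11.3 gives no survey analysis that would settle the matter.

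**Working it through.** **Which days carry which question (Section 8.1.6)**

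| Day | Who is surveyed | Preference comparison described |
|---|---|---|
| 1 | all LARs | application vs needle and syringe |
| 2 | all LARs | none listed |
| 8 | all LARs | post-patch period vs prior vaccination |
| 9 | patch 2/3 subset | as Day 8 |
| 15 | patch 2/3 subset | as Day 8 |
| 27–38 | all LARs | as Day 8 |

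The survey as a whole has 4 days for all LARs and 6 in the subset. The later preference question has 2 days for all LARs and 4 in the subset. Three preference days in all LARs are reached only by adding Day 1.

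**What the ANOVA phrase governs.** It ends the sentence on the 0–10 and 1–5 items. For those items, four common survey days in the same LAR suit a within-LAR analysis. The preference sentence names no analysis, and no other section plans an ANOVA of preference.

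**Is a bad choice forced?** No. Day 8 against the final call uses one question in all LARs. With two time points a repeated-measures ANOVA is the paired t-test: in one simulated data set with n = 25, F(1,24) = 3.303 and t² = 3.303, both with p = 0.0817.

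**What the feared analyses would cost.** The documents give no SD, correlation, uptake or significance level for the survey, so the inputs below are assumptions. The number of LARs (25 or 50) follows the planned enrolment.

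1. *Pooling Day 1 with Day 8 and final.* Let attitudes be constant and the Day 1 question shift the mean by d SD, with compound symmetry and correlation ρ. The noncentrality is n·(2/3)·d²/(1−ρ) on 2 and 2(n−1) df. For n = 25, d = 0.5, ρ = 0.5 it is 25 × 0.667 × 0.25 / 0.5 = 8.33, giving a rejection probability of 0.71 at the 5% level.

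| d (SD) | n = 25, ρ = 0.5 | n = 25, ρ = 0.3 to 0.7 | n = 50, ρ = 0.5 |
|---|---|---|---|
| 0 | 0.05 | 0.05 | 0.05 |
| 0.2 | 0.16 | 0.12–0.23 | 0.28 |
| 0.3 | 0.30 | 0.23–0.48 | 0.57 |
| 0.5 | 0.71 | 0.55–0.91 | 0.96 |

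2. *Comparing subset means on Days 9 and 15 with all-LAR means.* Let r be the correlation of opting in with its driver, u the uptake and φ(z)/u the usual selection factor. At u = 0.6 that factor is 0.644.
   - Opt-in driven by the Day 8 score: the shift is r·ρ·φ(z)/u = 0.5 × 0.5 × 0.644 = 0.16 SD. The range is 0.03–0.47 over r and ρ of 0.3–0.7 and u of 0.8–0.4.
   - Opt-in driven by a stable attitude: the shift is r·√ρ·φ(z)/u = 0.5 × 0.707 × 0.644 = 0.23 SD (range 0.06–0.57).

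3. *The usable contrast, Day 8 to final in all LARs.* The 95% half-width is t·√(2(1−ρ)/n). At ρ = 0.5 this is 2.064 × √(1/25) = 0.41 SD for 25 LARs and 2.010 × √(1/50) = 0.28 SD for 50. Over ρ from 0.3 to 0.7 it is 0.49–0.32 and 0.34–0.22 SD.

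**The case for a change.** The strongest case for acting is that Section 8.1.6 is the only place that names a survey analysis. If the ANOVA covers preference, it is ill-defined; if it does not, preference has no stated analysis. Either way the plan leaves open which items, days and LARs enter. The calculations also show that careless pooling could mislead. Even Day 8 to final mixes children who had further patches in between with children who did not. A few lines in Section 11.3 would cost almost nothing.

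The facts in this stand: the comparison changes after Day 1, Days 9 and 15 cover a selected subset, and Section 11.3 is silent on the survey. The step to a needed change does not.

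- Silence on the analysis of a descriptive secondary endpoint leaves description as the default. That is sound for preference on each day.
- The probabilities in item 1 belong to a test the plan does not propose, and they fall to 0.05 if the two questions have equal means.
- The shifts in item 2 arise when subset means are set against all-LAR means. In a within-LAR change, a shift from a stable attitude cancels. If opt-in follows the Day 8 score, some regression to the mean stays: r·(1−ρ)·φ(z)/u = 0.5 × 0.5 × 0.644 = 0.16 SD in the middle case. Section 8.1.6 already labels these surveys as belonging only to children with patches 2/3, so a reader would not take them for the whole sample.
- Asking about application on the day of application, and about the following period afterwards, is a natural design. A common preference question on every day would serve a time-course aim that the protocol does not state.

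**Conclusion.** The plan can be followed as written without error: a within-LAR ANOVA of the 0–10 and 1–5 items over the surveys all LARs complete, and a description of preference by day. Preference cannot be followed from Day 1 onward, or over three or more days in all LARs, on one question. That limits what can be reported but does not make a planned analysis wrong. An analyst with the questionnaire in hand would see that the Day 1 and later questions differ, keep them apart, use Day 8 (before patches 2/3) to final for any change, and show Days 9 and 15 as subset data. This is a gap that sensible practice fills, so no change to the plan follows.

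The conclusion rests on two readings. One is that the ANOVA phrase governs the items in its own sentence. The other is that those items are asked alike on the four common days; the questionnaire is not in the documents, so this cannot be confirmed. The protocol summary leaves the final call out of its list of survey times, but Sections 4, 7.6 and 8.1.6 and Appendix A include it, so the omission looks clerical.
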